2.3 Sample Size Considerations

Sample size calculations have been performed by simulations combined with normal approximation. Simulations assume the data follow exact Poisson distribution. Simulated data have been analyzed using Poisson regression without adjusting for overdispersion.

A total of 390 subjects will be randomized in a 1:1 ratio to one of 2 cohorts (Cohorts 1 or Cohort 2). Within each cohort, subjects will be randomized in a 2:1 ratio to receive SC tralokinumab (300 mg) or placebo. The primary analysis will be based on the ITT population.

Fifty-three subjects per treatment arm would be required to detect a 40% reduction in annual asthma exacerbation rate for each tralokinumab cohort compared to placebo assuming an annual exacerbation rate in placebo group of 1.2 with 80% power and a significance level of 0.1. Sample size was increased to 65 per treatment arm to accommodate overdispersion of 1.2. Recent data suggest that approximately half of asthmatic subjects may have a molecularly distinct subtype of asthma characterized by IL-13-driven inflammation; it is reasonable to hypothesize that these IL-13-positive subjects will have the optimal response to tralokinumab therapy. Therefore the sample size has been increased from 65 to 130 subjects per treatment arm to allow for a subanalysis to explore the relationship between the clinical response to tralokinumab and the presence of peripheral blood biomarkers associated with upregulation of IL-13 in the asthmatic lung. In the event that the clinical response is observed only in IL-13-positive subjects, this sample size retains adequate power to detect a difference in the asthma exacerbation rate comparing IL-13-positive tralokinumab treated subjects versus placebo. As presented below, the power to detect a 40% reduction in the exacerbation rate will depend upon the positive predictive value of the peripheral blood biomarker with respect to actual lung IL-13 expression (Table 1).

Table 1	Peripheral Blood Biomarker Positive Predictive Value
Table I	relipheral blood blomarker Positive Predictive value

Peripheral Blood Biomarker PPV	Two-sided alpha	Power (Individual Tralokinumab vs. Placebo)
100%	0.1	81.9%
90%	0.1	73.5%
80%	0.1	61.6%
75%	0.1	57.3%

IL-13 = interleukin-13; PPV = positive predictive value

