The following subgroups constitute subgroup populations of interest:

- 1) Subjects with percentage of predicted FEV1 at baseline $\leq 60\%$, and $\leq 80\%$;
- 2) Subjects with baseline % FEV1 reversibility (>= 12% and < 12%);
- Subjects with pre-bronchodilator FEV1 improvement at Week 5 and Week 13 (defined as percent change from baseline ≥ 10%) from tralokinumab group;
- 4) Subjects grouped by number of asthma exacerbations in the past year (2 vs > 2 but \leq 6 exacerbations);
- 5) Subject grouped by chronic OCS use (presence vs absence);
- 6) Subjects grouped by Th2 status (Th2-high: IgE >100 IU/mL and blood eosinophils $\geq 0.14 \times 10^{9}$ /L, and Th2-low);
- 7) Subjects grouped by atopic asthma status (atopic vs. non-atopic);
- 8) Subjects grouped by baseline serum periostin level (>= median or < median; ; >= 25^{th} percentile vs < 25^{th} percentile; >= 75^{th} percentile vs < 75^{th} percentile);
- 9) Subjects grouped by baseline peripheral blood eosinophil count (< 150 Cells/UL vs >= 150; < 300 Cells/UL vs >= 300).

The analyses described above except for comparisons between tralokinumab and placebo from the same cohort and for analyses for severe asthma exacerbations will be conducted for these subgroup populations.

For graphic presentation, cumulative number of asthma exacerbations and severe asthma exacerbations over time by treatment group, distribution of number of exacerbation by

Version 2.0

treatment group, forest plots of risk ratio (with 85% CI) for asthma exacerbations and severe asthma exacerbations for overall population and for each subgroup, and Kaplan-Meier curve of time to first asthma exacerbation and severe asthma exacerbation by treatment group will be created. Forest plots of risk ratio (with 85% CI) for asthma exacerbations and severe asthma exacerbations will also be created by baseline serum periostin level (< median, and >= Median; >= 25^{th} percentile vs < 25^{th} percentile; >= 75^{th} percentile vs < 75^{th} percentile) and by baseline peripheral blood eosinophil count (< 150 Cells/UL, 150 - < 300, and >= 300).

Summary	Population	Analysis
Summary of Asthma Exacerbation Rate through Week 53	ITT	Stage 1
Summary of Severe Asthma Exacerbation Rate through Week 53	ITT	Stage 1
Summary of Asthma Exacerbation Rate through Week 53	РР	Stage 1
Summary of Severe Asthma Exacerbation Rate through Week 53	РР	Stage 1
Summary of Asthma Exacerbation Rate between Week 53 and the End of Study	ITT	Stage 2

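### Section 3.5 analyses each subgroup separately and pre-specifies no formal comparison of the treatment effect between complementary subgroups

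*SAP*

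**What the plan says.** Section 3.5 specifies an overdispersed Poisson model with treatment group and covariate main effects. It yields rate ratios, 85% CIs and two-sided p-values for each tralokinumab regimen against combined placebo, and negative binomial, Cochran-Mantel-Haenszel and Cox analyses accompany it. The section then lists nine items under "The following subgroups constitute subgroup populations of interest" and says that these analyses, apart from the same-cohort and severe-exacerbation ones, "will be conducted for these subgroup populations". Forest plots with 85% CIs are planned for the overall population and each subgroup.

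No treatment-by-subgroup term, ratio of rate ratios or heterogeneity test appears in Section 3.5. The subgroup lists in Sections 3.6.2 (spirometry) and 3.6.3 (ACQ-6 and AQLQ(S)) do not add one.

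Section 2.3 explains that "the sample size has been increased from 65 to 130 subjects per treatment arm" in order to "allow for a subanalysis to explore the relationship between the clinical response to tralokinumab and the presence of peripheral blood biomarkers". It also raises the significance level for the data analysis from 0.1 to 0.15, two-sided. Section 3.1 bases the go/no-go decision on the overall population and sends subgroups defined by the lead serum biomarker candidates to a separate exploratory analysis plan.

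**The concern.** Whether response depends on periostin, eosinophils, Th2 status or OCS use is a question about the difference between two treatment effects. Section 3.5 produces the two effects and a p-value for each, but no estimate of how far they differ and no interval for that difference. A reader left with two p-values will tend to compare them. One significant half and one non-significant half is a common outcome even when the true effect is identical in both. At stake is a false predictive-marker signal that could steer the choice of population for a later trial.

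**Working it through.** **Inputs, all from SAP Section 2.3 unless noted.** The base calculation gives 53 per arm for a rate ratio of 0.6, "assuming an annual exacerbation rate in placebo group of 1.2 with 80% power and a significance level of 0.1". Allowing for overdispersion of 1.2 takes this to 65, and doubling gives 130 per arm, with combined placebo 65 + 65 = 130. The SAP supposes that "approximately half of asthmatic subjects may have a molecularly distinct subtype of asthma", which gives 130 / 2 = 65 per arm in each half. The analysis level is two-sided 0.15. Follow-up is 52 weeks (Section 3.5), taken as one year. The 0.9 placebo rate used below is an assumption: Section 2.3 says only that blinded estimates lie below 1.2.

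**Step 1: reproduce the plan's figures.** Wald test on the log rate ratio, with φ the overdispersion:

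n = φ (z₁₋α/₂ + z_power)² (1/λ₀ + 1/λ₁) / (ln RR)²

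With λ₀ = 1.2, λ₁ = 0.72, α = 0.10, 80% power:
- φ = 1: n = 52.7, so 53, as stated.
- φ = 1.2: n = 63.2, so 64, against the stated 65.

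For Table 1, RR = PPV × 0.6 + (1 − PPV), with 65 per arm, φ = 1.2 and α = 0.10:

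| PPV | RR | Recomputed power | Stated power |
|---|---|---|---|
| 100% | 0.60 | 81.0% | 81.9% |
| 90% | 0.64 | 72.7% | 73.5% |
| 80% | 0.68 | 63.1% | 61.6% |
| 75% | 0.70 | 57.9% | 57.3% |

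All agree within 2 points. Table 1 is therefore power for one test inside the positive stratum. No design figure concerns a difference between strata.

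**Step 2: separate tests in two halves with the same true effect.** Per half, SE² = φ [1/(65λ₀) + 1/(65λ₀RR)]. At λ₀ = 1.2 and RR = 0.60:
- SE² = 1.2 × (1/78 + 1/46.8) = 0.0410, so SE = 0.2026.
- Power at 0.15 = Φ(0.5108/0.2026 − 1.440) = 0.860.
- P(exactly one half significant) = 2 × 0.860 × 0.140 = 24%.

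At λ₀ = 0.9 the per-half power is 0.772, and 2 × 0.772 × 0.228 = 35%. With no effect anywhere, 2 × 0.15 × 0.85 = 25.5%.

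Other settings:
- For a 25/75 percentile split at rate 1.2, the stratum powers are 0.634 and 0.950, and exactly one is significant in 38% of trials.
- At 0.128, the final-analysis level in Section 3.1's example, the 24% becomes 27%.

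**Step 3: the comparator.** An interaction test at 0.15 declares a false difference in 15% of trials, whether the common effect is RR 0.60 or none.

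**Step 4: power of the interaction test.** For RR 0.6 in one half and 1.0 in the other, the two stratum variances add:
- λ₀ = 1.2: SE² = 1.2 × (1/78 + 1/46.8 + 2/78) = 0.0718, SE = 0.2679. Power = Φ(0.5108/0.2679 − 1.440) = 68%.
- λ₀ = 0.9: power = 58%.
- 80% power at rate 1.2 would need about 94 per arm per stratum.

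**Step 5: which items allow the comparison.** Items 2, 4, 5, 6 and 7 give one complementary split each, periostin gives three and eosinophils two: 5 + 3 + 2 = 10. Item 1 (at most 60% and at most 80% of predicted FEV₁, as printed) is nested. Item 3 is defined after baseline and only in tralokinumab subjects, so it has no placebo counterpart.

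**The case against.** The strongest reply is that the SAP never says subgroup effects are to be judged by p < 0.15 in one half and not the other. That is correct. A reader might infer such a rule from the 0.15 level in Section 2.3 and the 85% CIs, but no section states it, and the only decision rule given (Section 3.1) concerns the overall population.

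A reader might also infer that the plan cannot show differential response at all. That goes too far. The forest plots allow a visual comparison, and for disjoint strata the ratio of rate ratios can be derived from the two reported estimates and intervals. What is missing is a pre-specified formal comparison, not the information.

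Third, the biomarker question may be handled elsewhere. Section 3.1 sends the lead-candidate subgroups to an exploratory analysis plan that is not shown and may contain an interaction test. Section 3.7 makes the biomarker relationship an exploratory objective reported separately. Section 2.3's own power goal is a within-subgroup one, which a within-subgroup analysis serves. All of this stands, but periostin, eosinophils, Th2 status, OCS use and atopy have their method written in Section 3.5, and that method has no comparison between strata.

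Finally, the gain is moderate: 15% against 24% or 25.5%, not zero against a large number. Ten splits by two regimens give 20 interaction tests, of which 20 × 0.15 = 3 would fall below 0.15 by chance. This is why they need an exploratory label too.

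**Conclusion.** The point holds as a gap in pre-specification. Section 3.5 repeats main-effects analyses within each subgroup and plans no formal comparison of effects between complementary subgroups, although the sample was doubled to explore how response relates to biomarkers.

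If separate p-values were read at 0.15, a spurious contrast between halves would appear in about 24% of trials at the planned rate and effect, 35% at the assumed rate of 0.9, and 25.5% with no effect. These figures rest on a normal approximation without covariate adjustment, equal halves of 65 per arm and overdispersion 1.2.

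The documents do not support reading this as a flaw in the primary inference or in the overall-population go/no-go decision. Nor do they support any conclusion about subgroups assigned to the exploratory analysis plan. It is an inexpensive improvement to make before unblinding.

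**What to change.** For each of the ten complementary baseline splits (items 2 and 4 to 7, the three periostin cuts and the two eosinophil cuts), fit the overdispersed Poisson model on the full ITT population with treatment, split, treatment-by-split and the primary covariates. Where the split is already a covariate (past exacerbations, OCS use, atopy), only the interaction term is new. Report the ratio of rate ratios with its 85% CI and the interaction p-value for each regimen against combined placebo. Label these results and the within-subgroup p-values exploratory. Restate item 1 as complementary categories before including it, and leave item 3 out.

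The cost is a few lines of SAP text and ten extra models on data already collected. The downside is modest interaction power (Step 4), so the text should also say that a non-significant interaction does not show that the effect is the same in both strata.

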3.5 Summaries to Support the Primary Objective

The primary objective of this study is to evaluate the effect of two SC treatment regimens of 300 mg tralokinumab compared with combined placebo by assessing the asthma exacerbation rate over 52 weeks in adults with uncontrolled, severe asthma requiring high-dose ICS and LABA with or without additional controller medications. An asthma exacerbation is defined as a progressive increase of asthma symptoms (cough, wheeze, chest tightness, and/or shortness of breath) that does not resolve after the initiation of rescue medications and remains troublesome for the subject resulting in either 1) use of systemic corticosteroids (tablets, suspension or injection) or increase of a stable systemic maintenance dose for a duration of at least 3 consecutive days as prescribed or administered by the investigator or

healthcare provider; or 2) subject initiation of systemic corticosteroids for a duration of at least 3 consecutive days as outlined in the Asthma Action Plan provided to the subject by the investigator on Day 1 An asthma exacerbation event will be considered resolved 7 days after the last dose of OCS is administered (10 days after administration of an injectable corticosteroid). Courses of corticosteroids initiated after this time period would be considered a separate new asthma exacerbation.

Asthma exacerbation severity will be classified as follows:

- Moderate: Worsening symptoms requiring systemic corticosteroids for at least 3 consecutive days.
- Severe: Worsening symptoms requiring systemic corticosteroids and requiring urgent care evaluation and/or hospital admission.

Please note that a single depo-injectable dose of corticosteroid will be considered the equivalent to a 3-day course of systemic corticosteroids

The primary endpoint will be the annual rate of asthma exacerbations experienced by subjects after their first dose of investigational product up to their week 53 / Early Discontinuation visit.

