The crude asthma exacerbation rate will be estimated as a weighted mean (total number of exacerbations for the treatment group divided by the total duration of person follow-up) per the joint guidelines recommended by the ATS/ERS. The primary endpoint analysis will be conducted based on the ITT population using a Poisson regression model adjusted for overdispersion (Pearson Chi-Square correction) with treatment group, age, gender (male vs female), number of asthma exacerbations in the past year ($2 \text{ vs} > 2 \text{ but} \le 6 \text{ exacerbations}$), atopic asthma status (atopic vs. non-atopic), chronic OCS use (presence versus absence), and geographical region (United States/Canada/Western Europe, Eastern Europe, Asia, rest of world) as covariates and the log of number of days in the study as offset. Exacerbation rates, 85% CIs, rate ratios, 2-sided p-values will be provided based on the Poisson regression model. The primary endpoint will also be analyzed using a negative binomial regression model to assess the robustness with regard to the distributional assumptions. Pairwise comparisons between individual tralokinumab treatment group and combined placebo from Cohorts 1 and 2 will be conducted. Comparison between tralokinumab and placebo from the same cohort will be conducted as secondary analyses. Analysis based on the PP population will be performed as a sensitivity analysis.

The primary endpoint will also be analyzed using Cochran-Mantel-Haenszel row Mean Score Test. For analyses based on ITT Population, the adjusted number of exacerbations for subjects who withdraw from the study will be calculated using the following equation: [recorded number of exacerbations] / [number of days in the study] × 365.25.

Severe asthma exacerbations are of interest. The Analyses mentioned above will be conducted specifically for severe asthma exacerbations as well.

In addition, asthma exacerbations and severe asthma exacerbations between week 53 and end of the study, and asthma exacerbations and severe asthma exacerbations through the end of the study will also be summarized. Time to first exacerbation and time to first severe exacerbation will be analyzed as a supportive efficacy analysis to the primary objective. A Cox proportional hazard model will be fitted to data.

The number and proportion of subjects with different number of asthma exacerbations and severe asthma exacerbations (0, 1, 2, 3, and > 3) will be summarized by treatment group.

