The weekly morning and evening average of FEV₁ and PEF at home will be summarized by week. The weekly average along with change from baseline and percent change from baseline at various time points will be summarized using descriptive statistics. Diurnal PEF variability defined as 100% x (PM PEF - AM PEF)/((AM PEF +PM PEF)/2), i.e. amplitude % mean will be summarized by visit using descriptive statistics also.

Spirometry data will be summarized for the following subgroups:

- 1) Subjects with percentage of predicted FEV1 at baseline $\leq 60\%$, and $\leq 80\%$;
- 2) Subjects with baseline % FEV1 reversibility (>= 12% and < 12%);
- Subjects with pre-bronchodilator FEV1 improvement at Week 5 and Week 13 (defined as percent change from baseline ≥ 10%) from tralokinumab group;
- 4) Subjects grouped by number of asthma exacerbations in the past year (2 vs > 2 but \leq 6 exacerbations);
- 5) Subject grouped by chronic OCS use (presence vs absence);
- 6) Subjects grouped by Th2 status (Th2-high vs Th2-low);
- 7) Subjects grouped by atopic asthma status (atopic vs. non-atopic);
- 8) Subjects grouped by baseline serum periostin level (>= median or < median; >= 25th percentile vs < 25th percentile; >= 75th percentile vs < 75th percentile);
- 9) Subjects grouped by baseline peripheral blood eosinophil count (< 150 Cells/UL vs >= 150; < 300 Cells/UL vs >= 300).

Unacceptable spirometry data based on "Valid Best Test Review Result" will be excluded from the above analyses.

Absolute measurement over time, change from baseline over time, and percent change from baseline over time by treatment group will be graphed for the following spirometry measurement for overall and subgroups and for ITT population and PP population: pre- and post-bronchodilator FEV_1 (L) and pre-bronchodilator FVC (L).

Summary	Population	Analysis
Summary of Spirometry Results	ITT	Stage 1; Stage 2

MedImmune

Tralokinumab

Version 2.0

Change from Baseline in Spirometry Results	ITT	Stage 1; Stage 2
Percent Change from Baseline in Spirometry Results	ITT	Stage 1; Stage 2
Summary of Home Peak Flow Testing	ITT	Stage 1; Stage 2
Change from Baseline in Home Peak Flow Testing	ITT	Stage 1; Stage 2
Percent Change from Baseline in Home Peak Flow Testing	ITT	Stage 1; Stage 2
Summary of Change from Baseline in Spirometry Results at Week 53	ITT	Stage 1
Summary of Change from Baseline in Spirometry Results at Week 75	ITT	Stage 2
Summary of Spirometry Results	РР	Stage 1; Stage 2

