The overall and 4 domain scores from the AQLQ(S) responses along with their respective changes from baseline will be summarized using descriptive statistics by treatment group. Additionally, within each treatment group, the overall and 4 domain scores will be summarized by three categories, improvement (change in scores from baseline ≥ 0.5), no change (-0.5 \le change in score from baseline < 0.5), and worse (change in score < -0.5).

Mean ACQ-6 score over time and change from baseline in mean ACQ-6, overall AQLQ(s) score over time and change from baseline in AQLQ(s) over time will be plotted for overall and subgroups (see below) and for ITT population and PP population.

Subgroup analyses on ACQ-6 and AQLQ(s) will be conducted for the following subgroups:

- 1) Subjects with percentage of predicted FEV1 at baseline $\leq 60\%$, and $\leq 80\%$;
- 2) Subjects with baseline % FEV1 reversibility ($\geq 12\%$ and < 12%);

Version 2.0

- Subjects with FEV1 improvement at Week 5 and Week 13 (defined as percent change from baseline ≥ 10%) from tralokinumab group;
- 4) Subjects grouped by number of asthma exacerbations in the past year (2 vs > 2 but \leq 6 exacerbations);
- 5) Subjects grouped by chronic OCS use (presence vs absence);
- 6) Subjects grouped by Th2 status (Th2-high and Th2-low);
- 7) Subjects grouped by atopic asthma status (atopic vs. non-atopic);
- Subjects by serum baseline periostin level (>= median or < median; >= 25th percentile vs < 25th percentile; >= 75th percentile vs < 75th percentile);
- 9) Subjects grouped by baseline peripheral blood eosinophil count (< 150 Cells/UL vs >= 150; < 300 Cells/UL vs >= 300)

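### Subgroup 3 in SAP 3.5 selects tralokinumab subjects by on-treatment FEV1 response and stays in the placebo comparison, which can produce an apparent benefit with no drug effect

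*SAP*

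**What the plan says.** SAP section 3.5 lists nine subgroup populations. Items 1, 2 and 4 to 9 use baseline or pre-randomisation characteristics: lung function, reversibility, exacerbation history, chronic OCS use, Th2 status, atopy, periostin and eosinophils. Item 3 is "Subjects with pre-bronchodilator FEV1 improvement at Week 5 and Week 13 (defined as percent change from baseline ≥ 10%) from tralokinumab group".

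The sentence after the list fixes what is done in all nine: "The analyses described above except for comparisons between tralokinumab and placebo from the same cohort and for analyses for severe asthma exacerbations will be conducted". Those two exemptions are the only ones. What remains includes the main contrast, "Pairwise comparisons between individual tralokinumab treatment group and combined placebo from Cohorts 1 and 2 will be conducted", fitted with a "Poisson regression model adjusted for overdispersion (Pearson Chi-Square correction"), together with the negative binomial, Cochran-Mantel-Haenszel (CMH) and Cox analyses. Section 3.5 also calls for forest plots with 85% CIs for every subgroup. The outcome is counted "after their first dose of investigational product up to their week 53 / Early Discontinuation visit".

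The same item recurs in section 3.6.2 ("Spirometry data will be summarized for the following subgroups") and in section 3.6.3 ("Subgroup analyses on ACQ-6 and AQLQ(s) will be conducted for the following subgroups"), where it lacks the pre-bronchodilator qualifier.

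**The concern.** A subgroup contrast keeps the protection of randomisation only if membership is fixed before treatment and the rule applies alike in every arm. Item 3 meets neither condition. Three consequences follow if its members are compared with placebo.

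- Subjects whose FEV1 rises may also be those with less exacerbation-prone disease, on drug or on placebo. Picking them out in one arm only would then lower that arm's rate without any drug effect.
- The outcome window starts at first dose, so it overlaps the Week 1 to 13 window in which subjects are selected. An exacerbation before Week 13 counts as an event and may also depress the FEV1 reading that decides membership.
- A subject must be measured at the qualifying visit to be classified, so early withdrawals leave the tralokinumab side only.

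The resulting row would sit in the same forest plot as eight pre-treatment subgroups, with nothing to tell the reader that it is a different kind of estimate.

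**Working it through.** **1. Does the placebo comparison reach item 3?** The exemption sentence removes only same-cohort comparisons and severe-exacerbation analyses. Item 3 is not excluded, so the combined-placebo comparison and the forest plot apply to it.

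**2. Who is the comparator?** Section 3.5 does not say. Item 3 contains tralokinumab subjects only. Taken literally there is no placebo subject in the subgroup and no rate ratio. The natural way to carry out the instruction is responders against all placebo, and the rest of the check uses that reading.

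**3. Inputs from the SAP (sections 2.1, 2.3 and 3.5).** 130 subjects per tralokinumab arm; 65 + 65 = 130 combined placebo; planned placebo rate 1.2 per year, with blinded estimates lower; overdispersion 1.2; two-sided level 0.15, hence 0.15/2 = 7.5% nominal in the favourable direction.

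The plan's own sample size reproduces from these design values at its original two-sided 0.1:

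n = (1.645 + 0.842)² × (1/1.2 + 1/0.72) / (ln 0.6)² = 52.65, so 53 as stated. With overdispersion, 53 × 1.2 = 63.6, so 64 against the stated 65.

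**4. Assumptions not in the SAP.** True rate ratio 1; rates 0.5 to 1.2 per year; FEV1 change with mean 5% and SD 18%; between-visit correlation 0.6 for the both-visits rule; correlation 0 to 0.4 between FEV1 gain and lower exacerbation propensity. Subject-level frailty variance v is set so that overdispersion = 1 + rate × v = 1.2, giving v = 0.40, 0.25 and 0.167 at rates 0.5, 0.8 and 1.2.

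Under a single 10% threshold the selected share is P(Z ≥ (10 − 5)/18) = P(Z ≥ 0.278), about 0.39, or about 51 of 130.

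**5. Test.** Log rate ratio = ln(mean count in responders / mean count in placebo). SE = √[φ × (1/events in responders + 1/events in placebo)], with φ the Pearson estimate. Reject at |z| > 1.44. No covariates are fitted.

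**6. Results with no drug effect, overdispersion 1.2.**

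| Selection rule | Correlation | Apparent rate ratio | False benefit (nominal 7.5%) |
|---|---|---|---|
| Either rule | 0 | about 1.0 | about 7% |
| Single 10% threshold | 0.2 to 0.4 | about 0.91 to 0.77 | 15–29% |
| ≥10% at both visits | 0.2 to 0.4 | about 0.89 to 0.69 | 16–34% |

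The ends of the two ranges do not belong to one setting. The lowest ratios come at 0.5 per year, where the frailty variance is largest, while the rejection rate also depends on the number of events. A repeat of the single-threshold runs gave 0.92 to 0.76 and 15–31%, so the percentages are good to about two points. At correlation 0.1, false benefit is about 11%.

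**7. Variant at 1.2 per year, SD 15%, both visits** (27 to 30 of 130 selected). Correlation 0.2 gives 0.89 and 17%. Zero correlation gives 1.01 and 6.6%. Zero correlation plus an assumed 10-point FEV1 drop after a recent exacerbation gives 0.88 and 18%, which is the overlap of windows acting alone.

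**8. Is one-arm selection the cause?** Applying the same both-visits rule to placebo as well, in the variant of step 7 with correlations 0.2 to 0.5 and the acute drop, returns a rate ratio of 0.99–1.00 and total rejection of 14–16% at nominal 15%. The distortion therefore comes from selecting in one arm only.

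**9. Early withdrawal (not simulated).** For the CMH test, section 3.5 annualises withdrawals' counts. A placebo subject who leaves on Day 40 with one event scores 1/40 × 365.25 = 9.1. On the both-visits reading the matching tralokinumab subject cannot be in item 3.

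**10. FEV1 itself.** With no drug effect and zero correlation, the selected group already exceeds all placebo at Week 13 by about 17 percentage points (both visits) or 10 (either visit), under SD 15%. Across the correlations tried, the gap is 17–19 or 10–11 points.

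**The case against.** The best defence is that item 3 was meant as a description of early responders, that section 3.5 never says they are to be compared with all placebo, and that any size given for the bias is assumed.

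Much of this stands. The comparator is inferred. A reader might infer that the plan sets out responders against unselected placebo; it does not, and the defect on the page is a comparison ordered without a defined comparator. A reader might also infer that a false benefit is certain. The SAP gives no link between FEV1 change and exacerbations, and with none there is no material bias in the exacerbation rate. Larger figures are easy to obtain: a frailty variance of 0.8 gives ratios of 0.84 to 0.70 and false benefit of 17–46%, but it implies overdispersion of 1.40 at 0.5 per year and 1.64 at 0.8, above the plan's 1.2.

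Scope is limited too. Forest plots are specified only in section 3.5. Section 3.6.2 summarises spirometry, and the ANCOVA is optional and not assigned to subgroups. Section 3.6.3 is mainly descriptive apart from Fisher's exact test on ACQ-6 categories, and whether that test extends to subgroups is not stated. No passage plans an early-responder claim.

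The descriptive-intent defence does not stand. The SAP names two exemptions for the subgroup analyses, and item 3 is neither of them.

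**Conclusion.** The point holds as a conditional one. As written, item 3 leads either to a contrast that cannot be estimated or to one that randomisation does not support. On the second reading it can show a benefit with no drug effect, at roughly two to four and a half times the nominal 7.5% for assumed correlations of 0.2 to 0.4 at the SAP's own overdispersion. The invalidity of the contrast does not depend on those assumptions; its size does.

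For FEV1 in section 3.6.2 the selected group looks better by construction and no correlation is needed, but no subgroup test is prespecified there.

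It would be wrong to read this as a threat to the trial's main result. The primary ITT comparison is untouched, and section 3.1 rests go/no-go on the Stage 1 overall population. This is a correction that should be made to a supportive analysis.

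**What to change.** In section 3.5, exclude item 3 from the comparisons with placebo and from the forest plots. In sections 3.6.2 and 3.6.3, do not present it beside unselected placebo as a treatment contrast.

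If early response is of interest, replace it with a landmark table:

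- classify subjects in all arms, placebo included, by the same 10% rule at Week 13, and state whether the rule requires both visits or one;
- count only exacerbations after Week 13, among subjects still followed then;
- show rates by arm and responder status descriptively, labelled non-randomised, without p-values.

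The table should stay descriptive even with the same rule in every arm. Symmetric selection removes the bias under the null, but it does not give a causal subgroup effect if the drug itself changes FEV1.

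The cost is SAP wording and one replacement table, with no new data. Exacerbations before Week 13 are not used in that table.
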